**Utility of an Animated Bowel Biofeedback Training Routine to Improve Bowel
Function in Individuals With SCI**

NCT02406859

October 10, 2016

STUDY TITLE: Utility of an Animated Bowel Biofeedback Training Routine to Improve Bowel Function in Individuals with SCI

A. SPECIFIC AIMS

Biofeedback techniques are known to decrease the frequency of fecal incontinence (FI) in able-bodied (AB) populations and improve reflex defecation in persons who experience constipation. We hypothesize that bowel biofeedback training in spinal cord injured (SCI) patients will result in the following:

In subjects with decreased external sphincter strength and control (FI subjects): Improved objective bowel function parameters as measured by anorectal manometry, a decrease of FI episodes, a decrease in Wexner's incontinency score and a decrease in the SCI Bowel Surveys Score.

In subjects with tonic, constricted external sphincter and missing/decreased recto-anal inhibitory reflex (RAIR) (constipation subjects): An increase in sensitivity and strength of the RAIR and decreased symptoms of constipation (Bowel and Bladder Survey).

Specific Aims:

1. To assess baseline motility characteristics (resting pressure, squeezing pressure, high pressure zone, and RAIR) in persons with chronic SCI.
We hypothesize that individuals with SCI will have abnormal resting pressures (either increased or decreased, decreased squeezing pressures and an impaired RAIR reflex.
2. To determine the characteristics of SCI (level, completeness, baseline manometric parameters) which best predict the outcome of the biofeedback training. Additionally, we aim to assess the efficacy of bowel biofeedback therapy in SCI patients in improving:
 - a) Changes in maximum rectal and sphincter pressures generated during "squeeze" and "bear down" maneuvers performed during anorectal manometric studies pre-post treatment.
We hypothesize that due to the learning and conditioning effects of the biofeedback training, we will observe increases in generated sphincter pressures.
 - b) Changes to the sensitivity and strength of response of the RAIR reflex in response to rectal distension.
We hypothesize that the RAIR response will may be partially restored or strengthened by biofeedback training.
 - c) FI and constipation as assessed by the Bowel Surveys and Wexner's Incontinence Scale.
We hypothesize that biofeedback will improve subjective symptoms of FI, constipation, or both.

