For our pilot study, we are proposing the use of a 12 week biofeedback training to improve anorectal motility and voluntary control of the IAS, EAS and rectal musculature. It is unknown as to what level and completeness of SCI patients can expect to benefit from such treatment. As such, we are planning on enrolling all non-ambulatory SCI subjects with complete or incomplete injuries (ASIA A, B, C or D). Subjects will be enrolled only if they currently report problems with either constipation or FI on a based on survey responses (Ten Item SCI Bowel Survey (10 SCIB) and Wexner's Incontinency Scale (WIS). Anorectal motility pre to post biofeedback training will be performed. We aim to describe the anorectal pressure profile in persons with SCI and to identify responders to biofeedback training. We believe anorectal function will differ according to the level and completeness of injury. Additionally, we seek to define the levels and completeness of injury, and baseline manometric parameters which are predictors of treatment success.

C. PROCEDURES, METHODS AND EXPERIMENTAL DESIGN

This is a prospective, non-randomized, single center clinical trial. SCI patients will be stratified to 4 different arms according to the level of SCI:

- Upper motor neuron (UMN) incomplete (C5-T12)
- Lower motor neuron incomplete (LMN) (L2-S5)
- UMN complete (C5-T12)
- LMN motor neuron complete (L2-S5)

The Inclusion/Exclusion criteria are as follows:

Inclusion Criteria:

- Chronic SCI (duration over 1 year),
- Able-bodied (non-SCI)
- Between the ages of 18-75.

Exclusion Criteria:

- Contraindication to bowel biofeedback,
- Currently pregnant or trying to become pregnant,
- Inability to provide informed consent.

Study Population

Veterans from the JJPVAMC with chronic SCI, who are seen routinely in outpatient clinic and who complain of fecal incontinence or constipation (Screening Questionnaire: Appendix 1). Additional healthy AB veterans and/or non-veterans will be included in the study population as controls.

Recruitment and Enrollment:

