4. Assessment of the rectoanal inhibitory reflex (RAIR)- a balloon distension test will be performed. The rectal balloon attached to the pressure probe will be gradually filled with air starting at 30ccs and in 10cc increments until a RAIR reflex is identified. Balloon distension increases pressure registered by intrarectal sensors. The volume of air injected is displayed along with the pressure change it induced. Balloon distension normally produces a graded relaxation of the anal canal musculature. The RAIR reflex should appear as a relaxation of the IAS which starts on the rectal side of the anal canal which spreads caudally.

Manometric Parameters

RESTING	SQUEEZE
Maximum sphincter pressure	Maximum sphincter pressure

Mean sphincter pressure Length of IAS and EAS Length of anal verge to centre of anal canal BEAR DOWN Residual anal pressure Percentage anal relaxation Intrarectal pressure Rectoanal pressure differential	Duration of sustained squeeze BALLOON INFLATION (cc) Presence of rectoanal inhibitory reflex (RAIR) First sensation Urge to defecate Discomfort Minimum rectal compliance Maximum rectal compliance
---	--

The 10 Question Bowel Survey, SCI Bowel Management QOL, SCI Bladder Complication, SCI Bladder Management, and Wexner’s Incontinence Scale will be administered. A subgroup of 20 subjects who report either constipation or FI and who have an incomplete injury as defined by the ASIA Impairment Scale will be identified, and will have the option of enrolling in part 2 of the study; standard bowel biofeedback training.

[figure not shown]
Part 2: Biofeedback Training:

Once a subject has been identified as a candidate for biofeedback based on the ASIA examination (SCI incomplete ASIA B, C, D) and expressed interest in participation, an informed consent interview will be scheduled. Once written consent is obtained, a training schedule of twice weekly sessions will be scheduled. Twenty subjects will be recruited for this arm of the study. Each training session will last for approximately 60 minutes.

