Utility of an Animated Bowel Biofeedback Training Routine to Improve Bowel Function in Individuals With SCI

NCT02406859

March 10, 2013

Statistical Analysis Plan

For the continuous dependent, independent and demographic variables, descriptive statistics will be performed and expressed as group mean ± SD, with 95% confidence intervals and ranges. To examine the effect of the training on manometric and subjective parameters (groups: stratified by level of injury and completeness) analysis of variance (ANOVA) with repeated measures on visit (Pre, Post) will be performed. In the event of non-normal distribution of study outcomes, non-parametric ranking statistics will be applied as appropriate. An a priori level of significance will be set at P≤0.05. IBM SPSS Statistics version 22 will be used for all analyses.

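### The bowel surveys that help select trainees may also supply the Pre value, so the uncontrolled survey change can lean toward improvement and cannot be called efficacy

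*Protocol*

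**What the plan says.** **Selection.** The last paragraph of Protocol section B states: "Subjects will be enrolled only if they currently report problems with either constipation or FI on a based on survey responses". It names the Ten Item SCI Bowel Survey (10 SCIB) and Wexner's Incontinency Scale (WIS), and gives no cut-off. Section C, Part 1, lists the surveys given alongside manometry ("The 10 Question Bowel Survey, SCI Bowel Management QOL, SCI Bladder Complication, SCI Bladder Management, and" Wexner's scale). Its next sentence identifies "A subgroup of 20 subjects who report either constipation or FI", with an incomplete injury, as those who may enter Part 2.

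**Other routes into the study.** Section C, Study Population, describes patients "who complain of fecal incontinence or constipation (Screening Questionnaire: Appendix 1"). Part 2 describes a subject as "identified as a candidate for biofeedback based on the ASIA examination (SCI incomplete ASIA B, C, D") who has also expressed interest.

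**Measurement times.** After Part 1 the text goes to the Part 2 consent interview, scheduling and training. The next survey follows six weeks of in-house training and repeats Part 1. A third follows six weeks of home exercises.

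**Comparison.** The trial is non-randomized, and its four arms are injury strata. The able-bodied group supplies baseline values only. No follow-up of untrained SCI subjects is described.

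**Analysis and claim.** In the SAP, "analysis of variance (ANOVA) with repeated measures on visit (Pre, Post) will be performed", at a 0.05 level. It does not say which administration is Pre. Aim 2 says "we aim to assess the efficacy of bowel biofeedback therapy in SCI patients", and item (c) rests on the bowel surveys and the Wexner scale.

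**The concern.** People admitted because a symptom score was high on one occasion will, on average, score lower next time even if nothing has changed. This is because the first score partly reflects a bad spell or measurement error. If that first score is also the Pre value, the drop enters the Pre-to-Post change. A randomized or untreated comparison would show the same drop and cancel it, but this design has none.

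At stake is Aim 2c. The survey change would be biased toward benefit in expectation, the visit test would exceed its 5% level, and the result would be presented as efficacy. Manometric outcomes (Aims 2a and 2b) are not selection variables. This artefact reaches them only through their correlation with symptoms, although they too lack a control.

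**Working it through.** The plan gives no effect size, SD, reliability, cut-off or sample-size calculation, so there is no figure of its own to reproduce.

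**Inputs from the documents:** 20 trainees (Protocol, Part 2); significance level 0.05 (SAP; two-sided assumed).

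**Assumptions:** no training effect; normal scores, higher meaning worse; test-retest correlation r of 0.7 or 0.9; share qualifying q of 85%, 70%, 50% or 40%; a paired t-test on 20 differences, which equals the two-visit repeated-measures test when the injury-group factor is left out.

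**Model A: one score selects.** Expected spurious improvement in SD units is (1 − r) × φ(z) / q, where φ is the standard normal density and z is the cut that a share q exceeds. For r = 0.7:

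- q = 0.85: 0.3 × 0.233 / 0.85 = 0.08
- q = 0.70: 0.3 × 0.348 / 0.70 = 0.15
- q = 0.50: 0.3 × 0.399 / 0.50 = 0.24
- q = 0.40: 0.3 × 0.386 / 0.40 = 0.29

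For r = 0.9 each is one third as large: 0.03, 0.05, 0.08 and 0.10.

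**Model B: either of two independent scores selects.** This is closer to the constipation-or-FI rule, because a subject admitted for constipation has not been selected on the incontinence score. Here q is the share qualifying on at least one score. Correlated scores would fall between A and B.

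Simulated two-sided type I error (nominal 5%):

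| Share qualifying | A, r = 0.7 | A, r = 0.9 | B, r = 0.7 | B, r = 0.9 |
|---|---|---|---|---|
| 85% | 7% | 6% | 6% | 5% |
| 70% | 14% | 8% | 8% | 6% |
| 50% | 28% | 12% | 13% | 7% |
| 40% | 39% | 15–16% | 16% | 8–9% |

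The excess is almost all false improvement. In model A at r = 0.7 and q = 50%, essentially the whole 28% lies in that direction.

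**Effect of a second baseline.** If selection uses one score, and Pre and Post are later measurements equally correlated with it, the expected change under no effect is 0.00 SD. At q = 50% and r from 0.6 to 0.9, false improvement is 2.4% to 2.6% against a nominal 2.5%. If the repeat follows so soon that it correlates 0.9 with the selecting score while Post correlates 0.7 with it (and repeat with Post also 0.7), model A still gives about 9%, 14–15% and 19% at 70%, 50% and 40% qualifying. The matching values without a repeat are 14%, 28% and 39%.

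**The case against.** The strongest reply is that the double use of one score is not established. Enrolment is conditional on survey responses, while Part 1 surveys are given to people already consented, as a baseline assessment. Read literally, the enrolment response comes first and the Part 1 survey is already a second measurement, which is the remedy sought here. The selecting instrument is also uncertain. Study Population points to a separate screening questionnaire in Appendix 1, the outcome surveys are in Appendix 2, and Part 2 candidacy is described by ASIA examination and interest. Neither point can be settled from the text, so the concern is conditional. Equally, nothing displaces the explicit enrolment rule, and the SAP does not say which administration is Pre.

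A reader might infer several stronger things that the documents do not support:

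- **That narrowing 50 subjects to 20 is heavy selection on symptoms.** If every SCI enrollee already reports constipation or FI, the Part 2 symptom condition removes almost nobody. Injury completeness, interest and capacity do the narrowing, and any selection on symptoms enters mainly at enrolment.
- **That the 15% to 85% FI incidence in section B gives the qualifying share.** Those figures concern FI alone across studies. They are not the share meeting an either/or rule among patients who already complain. The cited 67% constipation and 85% FI suggest a high share and hence a small bias, but they come from motor-complete patients, whereas trainees have incomplete injuries.
- **That a spurious benefit is certain.** The bias holds in expectation. At 85% qualifying even the single-score model gives only 6% to 7%.
- **That a repeat baseline restores 5% in every case.** It does so only if the repeat is no more correlated with the selecting score than Post is.

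**Conclusion.** The concern holds in conditional form. If the enrolment or Part 1 score both selects and serves as Pre, the uncontrolled change in the Aim 2c surveys is biased toward improvement, and the planned test cannot separate this from a training effect. Under the assumptions above, type I error is about 6% to 39% when one score selects and about 5% to 16% when either of two independent scores does. The documents do not place the trial within those ranges, and the bias may be negligible if nearly everyone surveyed qualifies.

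The efficacy wording overclaims whatever the size of this artefact. Even with no selection on symptoms, a single-group change mixes training with time, attention and expectation. The remedy is cheap and does not depend on the missing inputs, so it is worth making.

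**What to change.** 1. Use the enrolment or Part 1 10 SCIB and WIS for eligibility only, and state in the protocol which instrument selects and when.
2. Re-administer both at the Part 2 consent interview or before the first training session. Name that value as Pre in the SAP for the outcomes on these two scales.
3. Report the change between the two baselines descriptively, as the change without training.
4. In Aim 2, replace the efficacy wording with *estimate the within-subject change after* biofeedback training. State that the design cannot separate training from time, attention or expectation effects.

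The second baseline removes most of the selection artefact; it does not address the effects named in step 4. The cost is two short questionnaires at a visit already planned, a few minutes of subject time, protocol and SAP wording, and a less favourable expected change.

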All training session will take place at the SCI Research Unit (Suite 7A-13). Subjects will be transferred onto a commode bed and asked to lie on their left side. A small disposable electromyography (EMG) plug electrode will be inserted into the rectal cavity, which will permit the subject to watch the trace of pelvic floor muscle activity (Figure 1) at rest, during voluntary contraction (squeeze) and during relaxation (bearing down). The subject will be asked to try to follow the visual prompts for approximately 30 minutes; for example, in the visual provided in Figure 1, the subject will be asked to try to guide the fish through the stream by voluntarily contracting and relaxing their pelvic floor muscles. These tracings will increase in levels of difficulty and complexity, as the subject is able accurately (< 10 percent error) reproduce the tracing in the level, within set times.

[figure not shown]
Response to balloon distension will be performed following the tracing exercises. The EMG

Figure 1: Biofeedback Visual

probe will be removed, and a pressure probe with EMG sensor will be inserted. An inflatable balloon will be at the distal end of each probe. The balloon will be distended to until an urge to defecate occurs or to a maximum of 150 ccs. The subject will be asked try and retain the balloon by squeezing the pelvic muscles. Based on each individual subject’s baseline abilities, between 5- 50 squeezes will be attempted/performed during the first sessions. Repetitions and target pressures will be increased from session to session based on individual gains. No more than 15 minutes will be spent on balloon distension trials. These sessions will be performed twice a week for 6 weeks. After 6 weeks of in-house training, each subject will undergo another manometric and survey study identical to Part 1 of the study. Subsequently, each subject will be sent home with a personalized training schedule, and will be asked to perform repetitions of squeezing and bearing down maneuvers two times a week. Each typical at home exercise program should last 30 minutes. After 6 weeks of home exercises, a third manometric study will be performed, and bowel surveys will be administered.

Study Timeline

We are proposing three year study duration.

Years 1 and 2: 25 SCI subjects for anorectal manometry; 5 AB subjects; and 10 incomplete SCI subjects for biofeedback training (per year).

Year 3: Results dissemination.

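### No follow-up is scheduled for trainees who stop, and the SAP's Pre/Post ANOVA would by default drop those without a Post value, so the training effect may describe completers only

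*Protocol*

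**What the plan says.** Protocol section C, Part 2 (Biofeedback Training), describes an in-house phase: "These sessions will be performed twice a week for 6 weeks". It then sets two follow-ups, each placed after a phase of training:

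- "After 6 weeks of in-house training, each subject will undergo another manometric and survey study identical to Part 1 of the study"
- "After 6 weeks of home exercises, a third manometric study will be performed, and bowel surveys will be administered"

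Neither document says what happens to the assessments of a trainee who stops.

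The SAP tests the training effect as follows: "analysis of variance (ANOVA) with repeated measures on visit (Pre, Post) will be performed". Its fallback is: "In the event of non-normal distribution of study outcomes, non-parametric ranking statistics will be applied as appropriate". It names no analysis population, missing-data method or dropout allowance. It has two visit levels where the protocol has three assessments, and it does not say which follow-up is Post.

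On size, Part 2 states: "Twenty subjects will be recruited for this arm of the study". On purpose, section B ends with: "We aim to describe the anorectal pressure profile in persons with SCI and to identify responders to biofeedback training". Aim 2 in section A adds the efficacy of training and the injury characteristics that predict its outcome.

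**The concern.** Timing an assessment by the end of a training phase leaves it unclear whether someone who quits that phase is ever assessed. A classical repeated-measures ANOVA needs every modelled visit for each subject, and so do paired rank tests. A trainee with a baseline but no Post value contributes nothing to the Pre/Post test.

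This matters here for three reasons.

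- Training has no untrained comparator. The able-bodied subjects are a comparison group for baseline measures only, so no parallel arm exists in which similar loss could offset the bias.
- With 20 trainees, each loss is 1/20 = 5% of the sample.
- Stopping is plausible. The in-house phase is 2 × 6 = 12 sessions of about an hour, each with a transfer to a commode bed and rectal probes, followed by six weeks of exercise at home.

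If those who stop tend to be those who are not improving, the mean change is too favourable. A baseline feature that predicts finishing could also look like a predictor of success.

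**Working it through.** **Who is lost.** There are two points at which a trainee can stop, and two possible meanings of Post.

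| Trainee stops during | Post = second assessment | Post = third assessment |
|---|---|---|
| In-house phase | likely no Post value, dropped | likely no Post value, dropped |
| Home phase | Post already measured, kept | likely no Post value, dropped |

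Loss of in-house stoppers does not depend on the meaning of Post. Loss of home-phase stoppers does.

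**Plan's own figures.** The documents give no power calculation, SD, effect size or dropout rate. The only figure to reproduce is the number of trainees: 10 per year × 2 years (Study Timeline) = 20, which agrees with Part 2.

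**Assumption.** A fraction p = 0.10, 0.20 or 0.30 of the 20 lacks a Post value, leaving 18, 16 or 14.

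**Overstatement if stoppers do not change.** With completer mean m, the all-starter mean is (1 − p)m + p·0 = (1 − p)m, so the ratio is 1/(1 − p):

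- p = 0.10: 1/0.90 = 1.11, or 11% too large
- p = 0.20: 1/0.80 = 1.25, or 25%
- p = 0.30: 1/0.70 = 1.43, or 43%

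**Loss of precision.** The paired change detectable with 80% power (noncentral t, two-sided 0.05) rises from 0.66 SD at n = 20 to 0.70, 0.75 and 0.81 SD at n = 18, 16 and 14.

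**Bias with no true effect.** In the simulation, 20 trainees have changes drawn from N(0,1). The chance of stopping falls with a better change (logistic, slope 1.0 per SD), calibrated to each p. Completers are tested with a paired t-test, which equals a one-group Pre/Post ANOVA.

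| p | Bias (SD) | False finding of benefit (nominal 2.5%) |
|---|---|---|
| 0.10 | 0.09 | 5.7% |
| 0.20 | 0.17 | 10.1% |
| 0.30 | 0.25 | 15.4% |

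Counting both tails, rejection runs from about 7% to 16% instead of 5%. A different dropout model (latent correlation 0.5 between change and staying) gives bias of 0.09, 0.17 and 0.24 SD and two-sided rejection of 7.2%, 10.9% and 15.2%.

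**Can analysis alone repair it?** In the same logistic scenario, a two-visit likelihood estimate that also uses baseline-only subjects, with an assumed pre-post correlation of 0.5, still has bias of 0.07, 0.13 and 0.20 SD. If baseline is unrelated to change, nothing is gained. Setting stoppers to no change still gives a false benefit in 5.7%, 10.0% and 14.9% of trials. Only measuring the stoppers removes the problem.

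**The case against.** The strongest reply is that the plan is silent on stoppers and does not exclude them. No complete-case rule is written, no minimum number of sessions is required, and the second assessment is written for each subject six weeks on, which can be read as a calendar visit for everyone. This stands: exclusion is a likely consequence of the silence and of the method's default, not a stated rule.

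A reader might infer more than the text supports:

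- **That a trainee who never exercises at home misses both follow-ups.** The second assessment comes before the home phase, so that trainee already has post-training data.
- **That the ANOVA requires all three assessments.** It has two levels only.
- **That a responder analysis is already distorted.** The protocol wants to identify responders but defines no responder endpoint. It also plans no replacement of stoppers.
- **That home practice goes unrecorded.** The protocol does not say whether it is logged.

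The magnitudes are also open to challenge. The dropout rate, the slope and zero change in stoppers are all assumed, and the simulation ties stopping to a final change that an early quitter has not yet experienced. The figures are therefore illustrations.

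Finally, this is a pilot, and an effect among those who complete training is a legitimate target if labelled as such. The plan does not label it so, and Aim 2 speaks of efficacy in SCI patients.

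**Conclusion.** The point holds as a gap with a probable direction. Followed as written, the plan is likely to lose trainees who quit in-house training from the efficacy result, and it loses home-phase stoppers only if Post is the third assessment. A reader might conclude that the SAP prescribes a completers-only analysis; it does not.

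The size depends on unknown dropout. At an assumed 10-30%, the overstatement is 11-43% if stoppers do not change. With no true effect and moderately outcome-related stopping, the bias is about 0.09-0.25 SD and two-sided rejection about 7-16% instead of 5%. If few stop, or stopping is unrelated to outcome, the bias is small and mainly precision is lost. The change is worth making because it is cheap and because, with a single trained group, nothing else in the design guards against this bias.

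**What to change.** 1. **Protocol, section C, Part 2 (the key step).** Assess every subject who starts training at 6 and 12 weeks after the first session, whatever training was done. From those who will not return for manometry, collect the bowel surveys and the Wexner scale by phone or mail. Their manometry will still be missing, and the report should say so.
2. **SAP.** Analyse all subjects who attend at least one session. Replace the two-level ANOVA with a likelihood-based mixed model over baseline, week 6 and week 12, so that a subject with baseline and one later visit is kept. Name in advance which contrast is the Pre-Post effect. Add a no-change sensitivity analysis, and state that the model alone does not remove bias from outcome-related dropout.
3. **Reporting.** Give the number who stop and the sessions attended. If a responder rate is reported, keep all starters in the denominator.

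The cost is a few sentences in each document and some phone or mail follow-up. No new subjects or procedures are needed. The effect estimate may come out less favourable.
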